8.5.4 Recording of concomitant drugs and therapies

The following information will be recorded regarding all concomitant drugs and therapies performed from the first day of the treatment period to completion of the follow-up observation period in the subject's CRF.

Information for the screening period will also be recorded in CRFs regarding drugs described in "8.5.2 Restricted concomitant medications and therapies."

The only information recorded about dialysis, drugs commonly used for dialysis (e.g., dialysate, anticoagulants, and substitution fluid), and physiological saline used for dissolving injectable formulations will be that specified in "9.2.1 Subject Background".

- (1) Concomitant drugs: Drug name, daily dosage, administration route, duration of administration, purpose
- (2) Concomitant therapies: Name of therapy, duration of treatment, purpose

8.6 Subject oversight

Investigators/subinvestigators, clinical coordinators, or study drug managers will oversee subjects with attention to the following points. Investigators/subinvestigators or clinical coordinators will question subjects about their adherence to the items below.

8.6.1 Drug use guidance for MT-6548 Tablet

Investigators/subinvestigators or study drug managers will give guidance to subjects covering the following items.

- (1) MT-6548 Tablets will be issued to subjects in bottles containing 100 tablets. If multiple bottles are issued at a time, subjects will open new bottles only after finishing the MT-6548 from the existing bottle. Subjects will bring all bottles of MT-6548 to each study visit for study drug control purposes, including unused bottles, bottles being used, and empty bottles.
- (2) MT-6548 Tablets are to be taken with water once-daily, without chewing. The drug does not need to be taken with meals, but timing should be as consistent as possible throughout the treatment period, both in relation to meals and time of day. If a subject forgets to take the study drug on a given day, they should resume taking the study drug as normal on the next day.
- (3) Oral iron supplements and iron-containing phosphate binders may impair MT-6548 bioavailability, so these must not be taken at the same time as MT-6548 Tablet. Subjects taking oral iron supplements or iron-containing phosphate binders will not take any within 2 hours before or after taking MT-6548 Tablet.

8.6.2 Visits

Subjects should make study visits as close to the same time as possible during the study period for scheduled tests.

8.6.3 Lifestyle guidance

Investigators/subinvestigators or clinical coordinators will give guidance to subjects covering the following points.

- (1) Subjects receive examinations and tests on scheduled days. Subjects should always contact the study center if unable to make a scheduled study visit, and follow instructions.
- (2) Subjects should contact investigators/subinvestigators in a timely manner if they experience abnormal symptoms.
- (3) Subjects will receive a study participation card to show when receiving care at other departments or hospitals. Subjects should always inform investigators/subinvestigators or clinical coordinators if they are using any drugs prescribed by other doctors or purchased at a pharmacy. Subjects should always consult with investigators/subinvestigators or clinical coordinators before using any new drugs during the study.
- (4) Maintain the same lifestyle (daily activities, food, etc.) as before to the extent possible.
- (5) Investigators/subinvestigators or clinical coordinators will instruct women who may become pregnant to use the contraception methods described below during the study period and up to 30 days following the final dose of the study drug, and men during the study period and up to 90 days following the final dose of the study drug. Calendar, anovulation, ovulation detection through body temperature, post-ovulation, and withdrawal do not constitute appropriate forms of contraception. This does not apply to postmenopausal women with absence of menstruation for more than 1 year, women with surgical hysterectomy, or women with bilateral ovariectomy.
 - 1) Abstain from intercourse
 - 2) Use two effective types of contraception. Joint use of a barrier method (latex condoms for men or diaphragm) in conjunction with a highly effective method such as oral contraceptives, IUD, tubal ligation, or vasectomy is recommended.

9. Tests and observations

9.1 Test and observation schedule

Item	Visit	Informed consent	Screening period [a]		Treatment period Phase 1												Treatment period Phase 2												Final day of the follow-up observations [c]	Day of discontinuation
			First day	Visit 2	W2	W4	W6	W8	W10	W12	W16	W20	W24	W28	W32	W36	W40	W44	W48	W52	W56	W60	W64	W68	W72	W76				
Visit number	IC	SV1	SV2	TV1	TV2	TV3	TV4	TV5	TV6	TV7	TV8	TV9	TV10	TV11	TV12	TV13	TV14	TV15	TV16	TV17	TV18	TV19	TV20	TV21	TV22	TV23	TV24	FU		
Permitted range (days)	-	-	-	-	-	-	-	-	-	-	-	-	-	-	-	-	-	-	-	-	-	-	-	-	-	-	-			
Procedure evaluation																											-7	+7 or +14 [d]		
Informed consent	X																													
Inclusion/exclusion criteria	X	X	X	X																										
Allocation					X																									
Patient background and history	X																													
Height					X																									
Dry weight, body weight [e]						X																								
Folic acid and vitamin B ₁₂ [f]					X																									
Pregnancy test [h]					X																									
Hematology test [f], [g], [i]					X [j]	X	X	X	X	X	X	X	X	X	X	X	X	X	X	X	X	X	X	X	X	X				
Blood biochemistry test [f], [g], [k]					X	X	X	X	X	X	X	X	X	X	X	X	X	X	X	X	X	X	X	X	X	X				
C-reactive protein [f], [k]					X																							X		
Iron-related measures [f], [k]					X	X	X	X	X	X	X	X	X	X	X	X	X	X	X	X	X	X	X	X	X	X				
Haptoglobin [f]					X	X	X	X	X	X	X	X	X	X	X	X	X	X	X	X	X	X	X	X	X	X				
EPO [k]					X	X	X	X	X	X	X	X	X	X	X	X	X	X	X	X	X	X	X	X	X	X				
VEGF [k]					X																							X		
DHEAS [k]					X																							X		
Vital signs [f], [k], [l]					X	X	X	X	X	X	X	X	X	X	X	X	X	X	X	X	X	X	X	X	X	X				
Resting standard 12-lead ECG [k], [m]					X																							X		
Fundoscopy [d]					X																							X		
Chest X-ray [d]					X																							X		
Duration of hemodialysis																												X		
QoL measures (EQ-5D-5L, KIDQOL)																												X		
AE investigation [k]																												X		
Blood sampling for PK testing																												X		
Blood sampling for genetic analysis [k]																												X		
Blood sampling for plasma protein binding test [p]						X																						X		
Product evaluation procedure																												X		
Investigation of concomitant medications/therapies																												X		
MT-6348 tablets [q], [f], [k]																												X		
Daraparin alfa injection [r], [i]																												X		
Iron supplements																												X		

Blood sampling for genetic analysis performed once as early as possible after Week 2 of treatment period
 Blood sampling for genetic analysis performed once as early as possible after Week 2 of treatment period
 Administered according to the dosage adjustment guidelines
 Administered according to the dosage adjustment guidelines
 Iron supplements administered to maintain a serum ferritin level of ≥ 100 ng/mL or a TSAT of $\geq 20\%$

- [a] Maximum screening period length is 6 weeks. Test results will be reviewed prior to transitioning from the first day of the screening period to screening period Visit 2, and from screening period Visit 2 to the first day of the treatment period. Re-testing will be performed as necessary.
- [b] During the treatment period, subjects are to visit the study site on the day of dialysis after a 2-day interdialytic interval; however, if this is difficult, subjects are to visit the study site on the day of dialysis after a 1-day interdialytic interval.
- [c] Not required if withdrawn prior to the treatment period.
- [d] Fundoscopy and chest X-ray performed once during screening period, once during Weeks 20–24 of treatment period, and once during Weeks 48–52 of treatment period. In the case of discontinuation of the treatment period, fundoscopy and chest X-ray should be performed within 14 days after discontinuation whenever possible.
- [e] Body weights should be measured before and after dialysis.
- [f] To be measured before dialysis on the day of dialysis during the screening period.
- [g] Tests during the treatment period should be performed before dialysis on the day of dialysis.
- [h] To be performed only in female subjects of childbearing potential.
- [i] Hb levels should be measured in blood collected in the supine position.
- [j] Only Hb levels should be measured.
- [k] Only urea nitrogen levels should be measured before and after dialysis on the first day, Weeks 24 and 52 of the treatment period, and on the day of treatment discontinuation.
- [l] To be measured in the sitting position after a 5-minute rest before blood sampling whenever possible.
- [m] To be measured in the supine position after a 5-minute rest before blood sampling whenever possible.
- [n] AE investigation begins after study drug administration.
- [o] For subjects giving consent to blood sampling for genetic analysis, blood will be collected once as early as possible after Week 2 of the treatment period.
- [p] For subjects giving consent to the plasma protein binding rate study, blood will be collected once before study drug administration on the day of dialysis before dialysis.
- [q] MT-6548 Tablets should be prescribed depending on the number of unused tablets by the subject. Subjects should be instructed to open a new bottle after using up the tablets in one bottle.
- [r] In principle, dosage adjustments should be performed at scheduled visits or on the day of darbepoetin alfa injection; however, an additional visit may be provided for dosage adjustment, if considered necessary, in cases where excessive increases or decreases in Hb levels are of concern based on the Hb time course.
- [s] The first dose should be administered after completion of the scheduled tests on the first day of

the treatment period.

- [t] The first dose should be administered after completion of the scheduled tests on the first day of the treatment period; however, the tests scheduled after dialysis should be performed before the first dose whenever possible.

If tests and observations cannot be performed on the scheduled day, they may be performed within the permitted ranges shown below. During the treatment period, subjects are to visit the study site on the day of dialysis after a 2-day interdialytic interval; however, if this is difficult, subjects are to visit the study site on the day of dialysis after a 1-day interdialytic interval.

Table 9.1-1 Permitted ranges for study center visits

Evaluation timepoint		Reference date	Permitted range
Screening period ^{*1}	First day	–	–
	Visit 2	–	–
Treatment period Phase 1	First day ^{*2}	Day 0	–
	Week 2	Day 14	Day 11–17
	Week 4	Day 28	Day 25–31
	Week 6	Day 42	Day 39–45
	Week 8	Day 56	Day 53–59
	Week 10	Day 70	Day 67–73
	Week 12	Day 84	Day 81–87
	Week 16	Day 112	Day 105–119
	Week 20	Day 140	Day 133–147
	Week 24	Day 168	Day 161–175
Treatment period Phase 2	Week 28	Day 196	Day 189–203
	Week 32	Day 224	Day 217–231
	Week 36	Day 252	Day 245–259
	Week 40	Day 280	Day 273–287
	Week 44	Day 308	Day 301–315
	Week 48	Day 336	Day 329–343
	Week 52	Day 364	Day 357–371
Day of discontinuation of treatment		Day of discontinuation	Within 7 days of discontinuation ^{*3}
Follow-up observation period	Day of completion	Week 52 of treatment period (or day of discontinuation of treatment period)	14–21 days

*1: Maximum screening period length is 6 weeks. Re-testing may be performed as necessary.

*2: The first day of the treatment period is the day that notification of subject suitability is received from the online enrollment system.

*3: Fundoscopy and chest X-ray to be performed to extent possible within 14 days of study withdrawal.

9.2 Test and observation timepoints

9.2.1 Subject background

The following subject background factors will be determined and recorded in the CRF.

- (1) Sex
- (2) Date of birth (western calendar)
- (3) Height
- (4) Race
- (5) Ethnicity
- (6) Smoking status
- (7) Underlying cause of CKD
- (8) Time of onset of nephrogenic anaemia
- (9) Concomitant illnesses (illnesses present on the first day of the treatment period)
- (10) Start time of hemodialysis
- (11) Type of hemodialysis*¹ (hemodialysis or hemodiafiltration)
- (12) Frequency of hemodialysis*¹ (times/week)
- (13) Hemodialysis conditions (dialyzer, dialysate, type of anticoagulant)
- (14) Type, administration route, dose interval, dosage, and final day of previous ESA formulation

*1: If the type of hemodialysis is changed at any point from the first day of the treatment period to the final day of the follow-up observation period, the date of the change and the type after the change should be recorded in the CRF.

*2: If the frequency of hemodialysis is changed at any point from the first day of the treatment period to the final day of the follow-up observation period, the date of the change and the frequency after the change should be recorded in the CRF.

9.2.2 Treatment status

9.2.2.1 MT-6548 Tablet

The following information should be recorded in CRFs.

- (1) MT-6548 dosage (details and reasons for change if there was a change of dosage or drug holiday)
- (2) First day of MT-6548 treatment and final day of MT-6548 treatment
- (3) MT-6548 treatment compliance status
- (4) Timing of MT-6548 doses (pre-prandial: within 30 minutes prior to eating; post-prandial: within 30 minutes of eating (including eating); other)
- (5) MT-6548 dose date and time*

* Date and time of dose immediately prior to blood sampling for EPO measurement at treatment period Weeks 2, 4, 12, 24, 36, 52, and day of discontinuation. Also, date and time for 2 doses immediately prior to blood collection for PK at treatment period Weeks 4, 12, and 24.

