Blood sampling and measurement will be performed for haematocrit and RBC count on the first day of the screening period, the first day of the treatment period, Weeks 2, 4, 6, 8, 10, 12, 16, 20, 24, 28, 32, 36, 40, 44, 48, and 52 of the treatment period, and the day of discontinuation of treatment.

(10) Reticulocytes (counts and fractions)

Blood sampling and measurement will be performed for reticulocytes (counts and fractions) on the first day of the screening period, the first day of the treatment period, Weeks 2, 4, 6, 8, 10, 12, 16, 20, 24, 28, 32, 36, 40, 44, 48, and 52 of the treatment period, and the day of discontinuation of treatment.

(11) EPO

Blood sampling and measurement of EPO will be performed on the first day of the treatment period, treatment period Weeks 2, 4, 6, 12, 24, 36, and 52, and the day of discontinuation of treatment. Blood sampling time will be recorded in CRFs.

EPO measurements will be disclosed to the sponsor after key code opening, but will not be disclosed to subjects, study center staff, or monitoring staff until completion of the final data

lock at the end of the study. Study centers are prohibited from measuring EPO during the treatment period in order to maintain blinding.

(12) QOL measures (EQ-5D-5L, KDQOL)

Subjects will fill out EQ-5D-5L and KDQOL questionnaires (Appendices 4 and 5) on the first day of the treatment period, treatment period Weeks 12, 24, and 52, and the day of discontinuation of treatment, and results recorded in CRFs.

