9.2.5 Pharmacokinetic-related endpoints

(1) Measuring plasma concentration

1) Blood sampling timing and volume

(a) Blood sampling timing: Treatment period Weeks 2, 12, and 24. [REDACTED]

[REDACTED]
[REDACTED]
[REDACTED]
[REDACTED]
[REDACTED]
[REDACTED].

(b) Blood sampling volume: [REDACTED]

(c) Number of times blood is sampled: 3 times

2) Blood processing

(2) Sample transport and storage

After the plasma drug concentration measurement sample is collected by the contract testing laboratory, it will be cryopreserved at -20°C or below. The contract testing laboratory will only send samples from subjects in the MT-6548 group to the drug concentration measurement laboratory, and will dispose of samples from subjects in the darbepoetin group.

Rationale

Blood will be sampled multiple times from each subject in order to evaluate fluctuation of levels within the body in a full population PK analysis. Three samples are to be collected from each subject also because of the paucity of data in Japanese people.

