10.3 Pharmacokinetics

Scatter plot diagrams for plasma concentrations of unchanged drug over time following MT-6548 Tablet treatment will be created.

11. Ensuring subject safety

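### The weeks at which Protocol 9.2.2.1 requires dose times do not match the PK draws in 9.2.5 (Week 4 against Week 2) or the EPO draws in 9.2.3(11) (Week 6 not covered)

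*Protocol*

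**What the plan says.** Protocol 9.2.2.1, item (5), has two rules on dose times.

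- For EPO, one dose time: "Date and time of dose immediately prior to blood sampling for EPO measurement at treatment period Weeks 2, 4, 12, 24, 36, 52". Discontinuation is on this list too.
- For PK, two dose times: "date and time for 2 doses immediately prior to blood collection for PK at treatment period Weeks 4, 12, and 24".

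The draws themselves are set elsewhere.

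- PK, in 9.2.5: "Blood sampling timing: Treatment period Weeks 2, 12, and 24", with "Number of times blood is sampled: 3 times".
- EPO, in 9.2.3(11): "measurement of EPO will be performed on the first day of the treatment period, treatment period Weeks 2, 4, 6, 12, 24, 36, and 52". Discontinuation is a further draw. The same item adds: "Blood sampling time will be recorded in CRFs".

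On use, Protocol 10.3 states: "Scatter plot diagrams for plasma concentrations of unchanged drug over time following MT-6548 Tablet treatment will be created". The rationale in 9.2.5 gives population PK analysis, and the scarcity of Japanese data, as the reasons for taking three samples per subject.

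**The concern.** A concentration or an EPO level measured after a once-daily oral dose is hard to read without knowing when the dose was taken. The protocol accepts this: it asks for two prior dose times with each PK sample and one with most EPO samples. The lists of weeks should therefore match the lists of draws, and they do not.

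A site that follows 9.2.2.1 literally would record paired dose times for a Week 4 PK draw that 9.2.5 does not schedule. It would not be required to record the pair at Week 2, where 9.2.5 does schedule one. At Week 6 the EPO clock time would be recorded with no dose time to set against it.

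There is also an operational risk. A site that takes 9.2.2.1 as the PK schedule might draw at Week 4 (Day 25–31 in Table 9.1-1) instead of Week 2 (Day 11–17). Protocol 13.2(5) and section 7.6 of the Phase 1 SAP send PK samples taken outside the permitted range to case review before use.

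**Working it through.** No power, error-rate or sample-size figure is involved. The check sets the lists of weeks side by side.

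**PK** (draws from 9.2.5; two-dose records from 9.2.2.1)

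| Week | PK draw | Two prior dose times required |
|---|---|---|
| 2 | yes | no |
| 4 | no | yes |
| 12 | yes | yes |
| 24 | yes | yes |

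Two of three draws match. Week 2 has a draw without the pair; Week 4 has the pair without a draw.

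**What Week 2 does have.** Week 2 is on the EPO dose-time list, so one prior dose time is required at that visit. The PK record therefore falls short by one of two times, not by both. The EPO dose time is also the last dose before the PK draw only if no tablet is taken between the EPO draw and the PK draw. The readable text does not say so.

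**EPO** (draws from 9.2.3(11); one-dose records from 9.2.2.1)

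| Visit | EPO draw | Prior dose time required |
|---|---|---|
| First day | yes | not needed (before first dose) |
| Weeks 2, 4 | yes | yes |
| Week 6 | yes | no |
| Weeks 12, 24, 36, 52 | yes | yes |
| Discontinuation | yes | yes |

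After the first day there are seven scheduled weeks plus discontinuation, so eight kinds of draw. Seven of the eight are covered; only Week 6 is not. Counting scheduled weeks alone, the gap is 1/7 = 14%.

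**Size for PK, if Week 2 is correct.** Planned MT-6548 subjects: 150 (Protocol 6.1). Samples: 150 × 3 = 450. At Week 2: 150 × 1 = 150, one third. This is a ceiling, because it assumes that every subject gives every sample.

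**Size for PK, if Week 4 is correct.** The draws would be {4, 12, 24} and the two-dose records {4, 12, 24}: three of three match and no PK dose time is lost. The error would then lie in 9.2.5.

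**Coverage once the lists are aligned:** 3 of 3 for PK and 8 of 8 for EPO.

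**The case against.** Four arguments point the other way.

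1. *Week 2 is not without a dose time.* This stands. A reader might infer from the mismatch that Week 2 PK samples have no dose time and cannot be interpreted. The documents do not support that, because the EPO rule secures one dose time at the visit. Tablets are taken once daily at a time kept as steady as possible, and dosage, compliance and timing relative to meals are recorded. These limit the loss from one missing earlier dose time.

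2. *Nothing readable shows which section is in error.* This stands. It is tempting to treat 9.2.5 as the authority and say that Week 4 in 9.2.2.1 is the slip. The readable text of the schedule tables does not settle the PK week, so the conclusion has to be conditional. The same holds in principle for Week 6 EPO: either list could be the wrong one.

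3. *Redaction.* Several lines directly after the PK weeks in 9.2.5 are blacked out, and the PK analysis text in 13.3.4 is partly redacted and refers to a separate protocol. Further timing rules may sit there. This could reduce the practical loss, but it does not remove the conflict between two lists that can be read. The CRF was not available either, so it cannot be said that the times would be unrecoverable.

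4. *No planned analysis is shown to fail.* For EPO this stands. EPO is among the other endpoints, and both SAPs analyse it by visit: descriptive statistics, a repeated-measures model, and a histogram at Week 24 (Phase 1 SAP 8.5.3(9)) or Week 52 (final SAP 8.5.2(9)). None of this uses time since dose. For PK, the one readable output is the plot in 10.3, which the single Week 2 dose time can serve subject to the condition above. The effect of a missing second dose time on the population PK model has not been quantified.

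**Conclusion.** The protocol contradicts itself on when dose times are collected. The PK rule in 9.2.2.1 and the PK draws in 9.2.5 disagree on one visit in three, and the EPO rule in 9.2.2.1 leaves out one of the scheduled EPO weeks in 9.2.3(11). As written, this is a wrong data-collection rule.

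If 9.2.5 is correct, the Week 2 PK sample lacks a requirement for the second prior dose time, affecting at most about 150 of 450 samples. If Week 4 is correct, no PK dose time is lost but 9.2.5 misdirects the draw. On EPO, if the Week 6 draw is intended, no dose time is required with it; this limits interpretation by time since dose and no more.

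The primary endpoint, the non-inferiority test and the sample size are unaffected. The conclusion rests on the readable text only, and redacted lines in 9.2.5 could soften the practical consequence. The point is still worth correcting, because the remedy is slight and a dose time not asked for at the visit may have to rest on recall.

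**What to change.** Check the PK and EPO rows of the schedule table in Protocol 9.1 and any redacted timing text in 9.2.5. Then reconcile 9.2.2.1, 9.2.5, 9.2.3(11) and the schedule so that:

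- two prior dose times are recorded at every PK draw;
- the preceding dose time is recorded at every post-dose EPO draw, including Week 6.

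If 9.2.5 and 9.2.3(11) are confirmed, the PK weeks in 9.2.2.1 become 2, 12 and 24, and Week 6 joins the EPO list. If Week 4 is confirmed for PK, 9.2.5 is the section to correct. Where EPO and PK blood are taken at the same visit, state whether one dose record serves both, which requires that no dose is taken between the two draws.

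Align the CRF with the result. The cost is protocol wording and the matching CRF fields; no visit or blood sample is added.
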